10.7.6 RETENTION OF RECORDS

The US FDA regulations (21 CFR §312.62[c]) and the ICH Guideline for GCP require that records and documents pertaining to the conduct of this study and the distribution of investigational drug, including eCRFs, ICFs, laboratory test results, and medication inventory records, must be retained by the Investigator for 2 years after the last marketing application approval in an ICH region or after at least 2 years have elapsed since formal discontinuation of clinical development of the study drug. All state and local laws for retention of records also apply. No records should be disposed of without the written approval of the Sponsor. Written notification should be provided to the Sponsor prior to transferring any records to another party or moving them to another location. For studies conducted outside the U.S. under a U.S. Investigational New Drug Application (IND), the Investigator must comply with the record retention requirements set forth in the US FDA IND regulations and the relevant national and local health authorities, whichever is longer.

All primary data, or copies thereof (e.g., laboratory records, eCRFs, data sheets, correspondence, photographs, and computer records), which are a result of the original observations and activities of the study and are necessary for the reconstruction and evaluation of any study report will be retained in the study site archives.

[figure not shown]

APPENDIX A – CLINICAL LABORATORY EVALUATIONS

Chemistry Panel (Fasted at least 8 hours):

Alanine aminotransferase
Albumin
Alkaline phosphatase
Aspartate aminotransferase
Blood urea nitrogen
Calcium
Chloride
Cholesterol
Creatinine
Creatine kinase (CK)/Creatine phosphokinase (CPK)
Glucose
Potassium
Sodium
Total bilirubin
Total protein
Triglycerides
Uric acid

Complete Blood Count:

Hematocrit
Hemoglobin
Mean corpuscular hemoglobin
Mean corpuscular hemoglobin concentration
Mean corpuscular volume
Platelet count
Red blood cell (RBC) count
RBC distribution width
White blood cell (WBC) count
WBC differential (absolute):
 Basophils
 Eosinophils
 Lymphocytes
 Monocytes
 Neutrophils

Urinalysis:

Bilirubin
Color and appearance
Glucose
Ketones
Leukocyte esterase
Nitrite
Occult blood
pH and specific gravity
Protein
Urobilinogen
Microscopic exam including bacteria, casts, crystals, epithelial cells, RBCs, and WBCs (if protein, leukocyte esterase, nitrite, or blood is positive)

Drug Screen:

Including but not limited to the following:
Alcohol (ethanol)^b
Amphetamines
Barbiturates
Benzodiazepines
Cannabinoids (THC)
Cocaine (metabolite)
Methadone
Opiates
Phencyclidine
Cotinine^a

Other Tests:

Hepatitis B virus core antibody^a
Hepatitis B surface antigen^a
Hepatitis C virus antibody^a
Human Immunodeficiency Virus antibody^a
Pregnancy test (females only; serum qualitative)
Follicle-stimulating hormone (FSH; postmenopausal females only)^a

^a Measured at the Screening visit only.

^b Alcohol breath testing will be performed at Check-in (Day -1) only.

APPENDIX B – APPROXIMATE MAXIMUM BLOOD VOLUME COLLECTED

Note: Additional samples may be drawn for safety purposes.

	Sample Volume (mL)	Number of Samples	Total Volume (mL)
Serology	7.0	1	7.0
Chemistry Laboratory Panel (includes serum pregnancy and FSH)	8.5	5	42.5
CBC (hematology)	4.0	5	20.0
PK Samples	4.0	30	120.0
		Total	189.5

CBC = complete blood count; FSH = follicle-stimulating hormone; PK = pharmacokinetic.

### 3 ABBREVIATIONS

Abbreviations pertain to the SAP only (not the TFLs).

ADaM	Analysis Data Model
AE	adverse event
AESI	Adverse events of special interest
AUC	area under the concentration-time curve
AUC 0-∞	area under the concentration-time curve extrapolated to infinity
AUC 0-t	area under the concentration-time curve calculated from Hour 0 to the last measurable concentration
BLQ	below the limit of quantification
CDISC	Clinical Data Interchange Standards Consortium
CI	confidence interval
CL/F	apparent systemic clearance
C max	maximum observed concentration
CSR	Clinical Study Report
CV	coefficient of variation
ECG	electrocardiogram
ICH	International Conference on Harmonisation
$\lambda_z$	apparent terminal elimination rate constant
MR AUC	metabolite ratio based on AUC 0-∞
NC	not calculated
NR	no result
PK	pharmacokinetic
QTc	QT correction; QT interval corrected for heart rate
QTcB	QTc calculated using the Bazett correction
QTcF	QTc calculated using the Fridericia correction
SAP	Statistical Analysis Plan
SD	standard deviation
t 1/2	apparent terminal elimination half-life
TEAE	treatment-emergent adverse event
TFLs	tables, figures, and listings
t max	time to maximum observed concentration
V z/F	apparent volume of distribution during the terminal elimination phase

## 4 INTRODUCTION

This SAP has been developed after review of the clinical study protocol (Final Version 1.0 dated 02 November 2018).

This SAP describes the planned analysis of the safety, tolerability, and PK data from this study. A detailed description of the planned TFLs to be presented in the Clinical Study Report (CSR) is provided in the accompanying TFL shell document.

The intent of this document is to provide guidance for the statistical analyses of PK data. In general, the analyses are based on information from the protocol, unless they have been modified by agreement between Genentech, Inc. and Covance Clinical Development Services. A limited amount of information concerning this study (e.g., objectives, study design) is given to help the reader's interpretation. This SAP must be finalized prior to the lock of the clinical database for this study. When the SAP and TFL shells are agreed upon and finalized, they will serve as the template for this study's CSR.

This SAP supersedes the statistical considerations identified in the protocol; where considerations are substantially different, they will be so identified. If additional analyses are required to supplement the planned analyses described in this SAP, they may be performed and will be identified in the CSR. Any substantial deviations from this SAP will be agreed upon between Genentech, Inc. and Covance EC Biometrics and identified in the CSR.

This SAP is written with consideration of the recommendations outlined in the International Conference on Harmonisation (ICH) E9 guideline entitled, "Guidance for Industry: Statistical Principles for Clinical Trials" and the ICH E3 guideline entitled, "Guidance for Industry: Structure and Content of Clinical Study Reports."

## 5 STUDY OBJECTIVES

The primary objective of this study is:

- To investigate the relative bioavailability of entrectinib F1 and F06 capsule formulations under fed conditions in healthy adult male and female subjects.

The secondary objective of this study is:

- To explore the safety and tolerability of a single 600-mg oral dose of entrectinib F1 and F06 capsule formulations in healthy adult male and female subjects.

## 6 STUDY ENDPOINTS

The primary endpoints are:

- The geometric mean ratios and associated 90% confidence intervals (CIs) of entrectinib and M5 metabolite PK parameters area under the concentration-time curve (AUC) extrapolated to infinity ( $AUC_{0-\infty}$ ) and maximum observed concentration ( $C_{max}$ ).

The secondary endpoints are:

- Incidence and severity of adverse events (AEs) and incidence of abnormalities in laboratory safety tests, 12-lead electrocardiograms (ECGs) and vital sign measurements.

[figure not shown]
## 7 STUDY DESIGN

This is a randomized, open-label, 2-treatment, 2-period, 2-way crossover study to investigate the relative bioavailability of entrectinib F1 and F06 capsule formulations under fed conditions in healthy male and female subjects. In each treatment period, subjects will receive a single 600-mg oral dose of entrectinib, provided as  $3 \times 200$ -mg capsules, after a standardized light meal. It is planned that a total of 14 subjects will receive the following 2 treatments in a randomized sequence:

- Entrectinib F1 capsule formulation (Test), fed
- Entrectinib F06 capsule formulation (Reference), fed

An overview of the study design is provided in [Figure 1](#):

**Figure 1 Overview of Study Design**

\* Minimum 14 days between study drug administrations in Periods 1 and 2

† Relative to study drug administration in Period 1

‡ Relative to study drug administration in Period 2

## 8 TREATMENTS

The following is a list of the study treatment abbreviations and ordering that will be used in the TFLs.

Study Treatment Name	Abbreviation	Treatment Order on TFLs
Entrectinib F1 capsule (Test)	F1	1
Entrectinib F06 capsule (Reference)	F06	2

The following is a list of the study treatment sequence abbreviations and ordering that will be used in the baseline TFLs.

Study Treatment Sequence	Abbreviation	Treatment Order on TFLs
Entrectinib F1 capsule (Test) / Entrectinib F06 capsule (Reference)	F1 / F06	1
Entrectinib F06 capsule (Reference) / Entrectinib F1 capsule (Test)	F06 / F1	2

## 9 SAMPLE SIZE JUSTIFICATION

A total of 14 subjects will be enrolled to ensure that 12 subjects complete the study and have evaluable PK data from both treatment periods.

The sample size has been chosen to ensure that the ratios of the geometric means for the PK parameters of entrectinib can be estimated with sufficient precision. In a previous study (Study RXDX-101-15), the within-subject coefficients of variation (CV) for  $AUC_{0-\infty}$  and  $C_{max}$  following administration of a single dose of entrectinib were estimated to be 20% and 16%, respectively. Based on a CV of 20%, with 12 evaluable subjects it is estimated that the lower and upper bounds of the 90% CIs of the ratio will be within 1.25x of the corresponding point estimates for each of the 2 entrectinib PK parameters ( $AUC_{0-\infty}$  and  $C_{max}$ ).

## 10 DEFINITION OF ANALYSIS POPULATIONS

The **Safety Population** will consist of all subjects who received at least 1 dose of study drug and have at least 1 postdose safety assessment.

The **PK Population** will consist of all subjects who received at least 1 dose of study drug and have at least 1 evaluable postdose PK sample. A subject may be excluded from the PK summary

statistics and statistical analysis if the subject has an AE of vomiting that occurs at or before 2 times median time to maximum observed concentration.

All protocol deviations that occur during the study will be considered prior to database lock for their severity/impact and will be taken into consideration when subjects are assigned to analysis populations. Details of subject assignment to the analysis populations will be listed.

The **All Subjects Population** will be consistent with the Safety Population.

## 11 STATISTICAL METHODOLOGY

### 11.1 General

Data listings will be provided for the All Subjects Population. Summary statistics and statistical analyses will be performed for subjects included in the relevant analysis populations (Safety/PK).

For continuous data, summary statistics will include the arithmetic mean, arithmetic standard deviation (SD), median, minimum, maximum, and number. For log-normal data (e.g., the PK parameters: AUCs and  $C_{max}$ ), the geometric mean and geometric CV will also be presented. For categorical data, frequency counts and percentages will be presented. Data listings will be provided for all subjects up to the point of withdrawal, with any subjects excluded from the relevant population highlighted. For the calculation of summary statistics and statistical analysis, unrounded data will be used.

Missing values will not be imputed, with the possible exception of missing PK predose concentrations, as detailed in Section 11.4.2.

Data analysis will be performed using SAS® Version 9.4.

Analysis Data Model (ADaM) datasets will be prepared using Clinical Data Interchange Standards Consortium (CDISC) ADaM Version 2.1, and CDISC ADaM Implementation Guide Version 1.1. Pinnacle 21 Community Validator Version 2.2.0 will be utilized to ensure compliance with CDISC standards.

#### 11.1.1 Definition of Baseline and Change from Baseline

Period specific baseline for each parameter is defined as the last value measured prior to dosing in each period, including repeat (vital signs and ECGs) and unscheduled (clinical laboratory parameters) readings (see [Section 11.1.2](#) for definitions of repeat and unscheduled readings).

Mean change from period specific baseline is the mean of all individual subjects' change from baseline values. Each individual change from baseline will be calculated by subtracting the individual subject's baseline value from the value at the timepoint. The individual subject's change from baseline values will be used to calculate the mean change from baseline using a SAS procedure such as Proc Univariate.

### **11.1.2 Repeat and Unscheduled Readings**

Repeat readings occur when the original vital signs or ECG result requires confirmation. Repeat readings are labelled as ‘Repeat’ in the listings and replace the original readings in all summaries and changes from baseline presentations and calculations. Prior to dosing, all readings taken in addition to the original reading are defined as predose repeats. Postdose repeat readings are defined as readings collected within 15 minutes of the actual time of the original reading.

With the exception of predose results described above, unscheduled readings for vital signs or ECGs are defined as readings collected >15 minutes from the actual time of the original reading. Unscheduled readings are labelled as ‘Unscheduled’ in the listings. Because unscheduled readings are not associated with any scheduled timepoint, they are excluded from all summaries (with the exception that they may be used as baseline, as stated in [Section 11.1.1](#)).

### **11.2 Demographics and Subject Disposition**

The demographic variables age, sex, race, ethnicity, body weight, height, and body mass index will be summarized and listed. Subject disposition will be summarized and listed.

### **11.3 Prior and Concomitant Medications**

Prior and concomitant medications will be coded using the World Health Organization (WHO) Drug Dictionary (Version September 2018 Enhanced Dictionary Version B3 format [or higher if version is updated during the study]). Prior and concomitant medications will be listed separately.

### **11.4 Pharmacokinetic Assessment**

#### **11.4.1 Pharmacokinetic Analysis**

The following PK parameters will be determined where possible from the plasma concentrations of entrectinib and M5 using non-compartmental methods performed using Phoenix WinNonlin (Certara USA, Inc., Version 6.4 or higher):

Parameter	Definition
$C_{\max}$	maximum observed concentration
$t_{\max}$	time to maximum observed concentration
$AUC_{0-t}$	area under the concentration-time curve calculated from Hour 0 to the last measurable concentration, calculated using the linear trapezoidal rule for increasing concentrations and the logarithmic rule for decreasing concentrations
$AUC_{0-\infty}$	area under the concentration-time curve extrapolated to infinity, calculated using the formula: $AUC_{0-\infty} = AUC_{0-t} + (C_t/\lambda_z)$ where $C_t$ is the last measurable concentration and $\lambda_z$ is the apparent terminal elimination rate constant
$\lambda_z$	apparent terminal elimination rate constant, where $\lambda_z$ is the magnitude of the slope of the linear regression of the log concentration versus time profile during the terminal phase
$t_{1/2}$	apparent terminal elimination half-life (wherever possible), where $t_{1/2} = \text{natural log}(\ln)2/\lambda_z$
$CL/F$	apparent systemic clearance, calculated as dose/ $AUC_{0-\infty}$ (entrectinib only)
$V_z/F$	apparent volume of distribution during the terminal elimination phase, calculated as $CL/F/\lambda_z$ (entrectinib only)
$MR_{AUC}$	metabolite ratio based on $AUC_{0-\infty}$ (M5 only)

Additional PK parameters may be determined where appropriate.

The PK analysis will, where possible, be carried out using actual postdose times recorded in the raw data. If actual times are missing, nominal times may be used with sponsor approval.

Concentrations will be used as supplied by the analytical laboratory for PK analysis. The units of concentration and resulting PK parameters, with amount or concentration in the unit, will be presented as they are received from the analytical laboratory.

The  $C_{\max}$  and  $t_{\max}$  will be obtained directly from the plasma concentration-time profiles.

For multiple peaks, the highest postdose concentration will be reported as  $C_{\max}$ . In the case that multiple peaks are of equal magnitude, the earliest  $t_{\max}$  will be reported.

The metabolic ratio ( $MR_{AUC}$ ) will be calculated as follows:

$$MR_{AUC} = \frac{AUC_{0-\infty} \text{ metabolite}}{AUC_{0-\infty} \text{ parent drug}}$$

The  $AUC_{0-t}$  or other common partial area may be used to determine  $MR_{AUC}$  if  $AUC_{0-\infty}$  cannot be reliably calculated for the majority of subjects.

#### 11.4.2 Criteria for Handling Concentrations that are Missing or Below the Limit of Quantification in Pharmacokinetic Analysis

- Concentration values that are below the limit of quantification (BLQ) will be set to zero, with defined exceptions as follows;
  - Any embedded BLQ value (between 2 quantifiable concentrations) and BLQ values following the last quantifiable concentration in a profile will be set to missing for the purposes of PK analysis.
  - If there are late positive concentration values following 2 BLQ concentration values in the apparent terminal phase, these values will be evaluated. If these values are considered to be anomalous, they will be set to missing.
  - If an entire concentration-time profile is BLQ, the profile will be excluded from the PK analysis.
  - If a predose concentration is missing, it may be set to zero.

#### 11.4.3 Criteria for the Calculation of an Apparent Terminal Half-Life

##### 11.4.3.1 Number of Data Points

- At least 3 data points will be included in the regression analysis and preferably should not include  $C_{max}$ .

##### 11.4.3.2 Goodness of Fit

- When assessing terminal elimination phases, the adjusted coefficient for determination of exponential fit ( $R^2$  adjusted) will be used as a measure of the goodness of fit of the data points to the determined line.
- Regression-based parameters (i.e.,  $\lambda_z$ ,  $t_{1/2}$ ,  $AUC_{0-\infty}$ ,  $CL/F$ ,  $V_z/F$ ,  $MR_{AUC}$ ) will only be calculated if the  $R^2$  adjusted value of the regression line is  $\geq 0.7$ .

##### 11.4.3.3 Period of Time Estimation

- The time period used for the estimation of  $t_{1/2}$  will be over at least 2 half-lives, where possible.
- Where an elimination half-life is estimated over a time period of  $< 2$  half-lives, it will be flagged in the data listings at the discretion of the Pharmacokineticist, and the robustness of the value should be discussed in the study report.

#### 11.4.3.4 Calculation of AUC

- The minimum requirement for the calculation of AUC will be the inclusion of at least 3 consecutive plasma concentrations above the lower limit of quantification, with at least 1 of these concentrations following  $C_{\max}$ .
- For any partial AUC determination (where applicable), nominal time will generally be used for the end of the interval. Actual times for partial AUC intervals may be used at the discretion of the Pharmacokineticist.
- The  $AUC_{0-\infty}$  values (and related parameters [CL/F,  $V_z/F$ ,  $MR_{AUC}$ ]) where the percentage extrapolation is less than 30% will be reported. Any  $AUC_{0-\infty}$  values (and related parameters) where the percentage extrapolation is  $\geq 30\%$  will be reported and flagged but excluded from descriptive statistics.

#### 11.4.3.5 Anomalous Values

- If a value is considered to be anomalous due to being inconsistent with the expected PK profile, it may be appropriate to exclude this point from the PK analysis. However, the exclusion of data must have strong justification and will be documented in the raw data and study report.
- Embedded BLQ values may be considered anomalous depending on the route of administration and the characteristics of the drug.
- If a PK profile has a quantifiable predose value that is  $>5\%$  of its respective  $C_{\max}$  value, all concentrations and PK parameters for the given PK profile may be excluded from the summary statistics of PK tables and statistical analysis at the discretion of the Pharmacokineticist.

### 11.4.4 Presentation of Pharmacokinetic Data

#### 11.4.4.1 Presentation of Pharmacokinetic Concentration Data

- The following rules will be applied if there are values that are BLQ or if there are missing values (e.g., no result [NR]) in a plasma concentration data series to be summarized.
  - For the calculation of summary statistics, BLQ values will be set to zero.
  - If an embedded BLQ value is considered anomalous within the concentration-time profile, this value will be excluded from the summary statistics.
  - Where there is NR, these will be set to missing.

- If there are <3 values in the data series, only the minimum, maximum and number will be presented. The other summary statistics will be denoted as not calculated (NC). A BLQ is considered a value.
- If all the values are BLQ, then the arithmetic mean, arithmetic SD, median, min and max will be presented as zero, and the geometric mean and geometric CV will be denoted as NC.
- If the value of the arithmetic mean or median is BLQ, it will be presented as zero, and the geometric mean and geometric CV will be denoted as NC.

#### 11.4.4.2 Presentation of Pharmacokinetic Parameters

- For the calculation of summary statistics of PK parameters, all NR and NC values in a data series will be set to missing.
- The AUC values will be set to NC if they have been calculated using fewer than 3 concentrations, and/or 3 concentrations if the last is  $C_{max}$ .

#### 11.4.5 Pharmacokinetic Statistical Methodology

Descriptive statistics (mean, median, minimum, maximum, SD, geometric mean, and geometric CV) will be calculated for all PK parameters and PK concentration data.

Plasma concentrations of entrectinib and its active metabolite M5, and derived plasma PK parameters, will be listed and summarized by treatment using descriptive statistics. Individual and mean concentration versus time profiles will be plotted.

The primary parameters for analysis will be  $C_{max}$  and  $AUC_{0-\infty}$  of entrectinib and M5.  $AUC_{0-t}$  or other common partial area may also be analyzed if  $AUC_{0-\infty}$  cannot be reliably calculated for the majority of subjects. A linear mixed model will be applied to analyze the log-transformed primary PK parameters. The model assumes fixed effects for treatment, period, and sequence, and a random effect for subject within sequence. Estimates of geometric mean ratios on the original scale, together with the corresponding 90% CIs, will be derived for the comparisons between Test and Reference treatments.

Example SAS code that will be used:

```
proc mixed data=xxx;  
class treatment period sequence subject;  
model lpk = treatment period sequence / htype=3 ddfm=kr;  
random intercept / subject=subject(sequence);  
lsmeans treatment / diff cl alpha=0.1;  
ods output lsmeans=lsmean diffs=diff;  
run;
```

Within-subject CV will be calculated for  $AUC_{0-\infty}$  and  $C_{max}$  based on the log-normal distribution using the following formula:

$$CV_w(\%) = [\exp(\text{mse}) - 1]^{1/2} \times 100$$

where mse is the residual error from the mixed model.

Residual plots will be produced to assess the adequacy of the model.

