9.4 STATISTICAL ANALYSIS OF PHARMACOKINETIC DATA

Descriptive statistics (mean, median, minimum, maximum, standard deviation, geometric mean, and geometric coefficient of variation [CV]) will be calculated for all PK parameters and PK concentration data.

Plasma concentrations of entrectinib and its active metabolite M5, and derived plasma PK parameters, will be listed and summarized by treatment using descriptive statistics. Individual and mean concentration versus time profiles will be plotted.

The primary parameters for analysis will be C_{max} and $AUC_{0-\infty}$ of entrectinib and M5. A linear mixed model will be applied to analyze the log-transformed primary PK parameters. The model assumes fixed effects for treatment, period, and sequence, and a random effect for subject within sequence. Estimates of geometric mean ratios on the original scale, together with the corresponding 90% CIs, will be derived for the comparisons between Test and Reference treatments.

All calculations will be performed using SAS[®] version 9.4 or greater.

Specification of PK parameters for analysis; criteria for study termination; procedures for accounting for missing, unused, or spurious data; procedures for reporting deviations from the original statistical plan; and selection of subjects to be included in the analyses population(s) will be presented in the CSR and/or SAP, as appropriate.

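### Does the example SAS code in SAP 11.4.5 turn the Test/Reference ratio upside down?

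*SAP*

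**What the plan says.** Protocol 9.4 and SAP 11.4.5 plan a mixed model on the log scale for Cmax and AUC0-∞ of entrectinib and M5. Geometric mean ratios with 90% confidence intervals "will be derived for the comparisons between Test and Reference treatments". Neither document writes out the numerator and denominator.

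SAP 11.4.5 introduces its program as "Example SAS code that will be used". The lines that matter here are "proc mixed data=xxx", "class treatment period sequence subject" and "lsmeans treatment / diff cl alpha=0.1". There is no ORDER= option, control level or ESTIMATE statement. The input dataset is a placeholder, and the values of `treatment` are not defined. The program saves the LS means and their differences and ends there, with no exponentiation step.

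SAP section 8 gives Test the abbreviation F1 and order 1, and Reference the abbreviation F06 and order 2. It states the scope of that table: "The following is a list of the study treatment abbreviations and ordering that will be used in the TFLs".

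**The concern.** By default PROC MIXED orders class levels by their sorted formatted values, and a plain DIFF subtracts the later level from the earlier one. As text, F06 comes before F1 because 0 sorts before 1. The full treatment names in SAP section 8 sort the same way, and so do the letters R and T from which Protocol 4.1 builds its sequence names. A programmer who used any of these as values of `treatment` would obtain Reference minus Test.

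The study has no equivalence criterion, so the estimate and its direction are the result. Protocol 2.2 wants the ratio to support dosing recommendations for F06 in children. It also says that F1 behaved differently from F2A in certain circumstances, while F2A and F06 are bioequivalent. A ratio away from 1 is therefore plausible, and an unnoticed inversion would reverse the conclusion about which capsule gives the higher exposure. The roles are easy to confuse as well, since Test is the capsule already used in children and Reference is the one intended for the market.

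**Working it through.** **1. The plan's own precision figure.** Inputs from SAP section 9: within-subject CV 20% (AUC0-∞) and 16% (Cmax), 12 evaluable subjects, 90% CI, stated bound 1.25-fold.

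- Log-scale within-subject SD: s = √ln(1 + CV²) = √ln(1.04) = 0.198.
- Standard error of the treatment difference: s × √(2/12) = 0.0809.
- CI factor with 10 degrees of freedom: exp(1.812 × 0.0809) = 1.158. At CV 16% it is 1.125.

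Both are within 1.25, so the plan's figure is reproduced.

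**2. Direction under each possible coding.** The labels were sorted and the earlier-minus-later rule was applied. SAS itself was not run.

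| Coding of `treatment` | First level | Difference returned |
|---|---|---|
| F1 / F06 (SAP section 8 abbreviations) | F06 | Reference − Test |
| Full names in SAP section 8 | F06 | Reference − Test |
| T / R | R | Reference − Test |
| Order numbers 1 / 2 in SAP section 8 | 1 = F1 | Test − Reference |

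Character 1/2, or letters A/B assigned in the section 8 order, would also put Test first. The direction therefore depends on a coding that the SAP does not give.

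**3. What an inversion does to the numbers.** The true ratio of 0.80 is an assumption made for illustration; no document gives one. CV 20%, n = 12.

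- Test/Reference: 0.80, with limits 0.80 / 1.158 = 0.691 and 0.80 × 1.158 = 0.926.
- Reference/Test: 1 / 0.80 = 1.25, with limits 1 / 0.926 = 1.080 and 1 / 0.691 = 1.447.

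Other assumed ratios behave in the same way: 0.70 (0.605 to 0.810) becomes 1.429 (1.234 to 1.654), and 0.90 (0.777 to 1.042) becomes 1.111 (0.960 to 1.286). On a simulated 12-subject crossover, Test − Reference gave 0.851 (0.802 to 0.904) and Reference − Test gave 1.175 (1.107 to 1.248). These are reciprocals with the limits exchanged. The CI factor is the same either way, so precision and coverage are unaffected.

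**4. Whether an inversion could reach the report unseen.** The `diff` dataset identifies both levels of each difference. The same program saves the LS mean for each treatment, and SAP 11.4.5 requires geometric means by treatment. With complete data and equal sequence sizes (an assumption), the difference in LS means equals the difference in mean logs. The tabulated F1 geometric mean divided by the F06 one then equals the model ratio exactly. In the illustration, the tables would show F1 at 0.80 of F06 beside a ratio labelled F1/F06 of 1.25. Unequal sequences or missing periods loosen that equality, but the LS means from the same model still show the direction.

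**The case for a change.** The best case for a change is that a prespecified plan should not depend on someone noticing. The direction of the primary endpoint is written nowhere. The code is described both as an example and as what will be used, and each set of text labels in the documents puts Reference first. Section 8 limits its order numbers to the tables, so they cannot be assumed to code the model variable. A ratio of 1.25 looks as credible as 0.80, so the number alone would not reveal the error. One added line would remove the risk.

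Part of this stands. The direction is indeed not written out, and naming F1/F06 as the ratio would do no harm. The limit on section 8 applies equally to both sides, however: if its order numbers cannot be taken as the coding, neither can its abbreviations, and the claim that the code returns the reciprocal needs those abbreviations. The code produces only a log-scale difference, so a further step is unavoidable, and the sign can be settled there. Harm requires both a mislabelled contrast and a failure to compare it with the means by treatment. SAP section 4 places the detailed table layouts in a separate shell document that was not available here, so how the ratio is labelled there is unknown.

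The obvious code change also depends on the unstated coding: `diff=control('F06')` works only if the formatted level is F06, and under 1/2 coding it matches no level.

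**Conclusion.** The concern does not call for a change. It is correct that the code fixes no direction and that coding `treatment` with the text labels F1 and F06 would give Reference minus Test. The documents do not show that this coding will be used, or that an unprocessed difference would be reported. The Test and Reference designations make Test/Reference the natural reading, and an analyst working from the plan would orient and label the ratio accordingly.

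The effect on the result is nil. The reciprocal carries the same information, with a CI factor of 1.158 at CV 20% and 12 subjects in both directions. The residual risk is a labelling slip that the level names and the means by treatment would expose. This conclusion assumes that the reported ratio is labelled with its two products and read alongside those means.
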